6.0 REGULATORY CONSIDERATIONS

6.1 Protection of Human Subjects

The Investigator must ensure that patients or their legally acceptable representatives are clearly and fully informed about the purpose, potential risks and other critical issues regarding clinical trials in which they volunteer to participate. Preparation of the consent form is the responsibility of the Investigator and must include all elements required by CFR 21 Part 50.25 and the local IRB.

6.2 Compliance with the Protocol and Protocol Revisions

The study must be conducted as described in this approved protocol. All revisions to the protocol must be provided to the PI. The PI should not implement any deviation or change to the protocol without prior review and documented approval/favorable opinion from the IRB/IEC of an Amendment, except where necessary to eliminate an immediate hazard(s) to study patients.

The investigator must ensure that patients or their legally acceptable representatives are clearly and fully informed about the purpose, potential risks and other critical issues regarding clinical trials in which they volunteer to participate. Preparation of the consent form is the responsibility of the PI.

6.3 Registration and Enrollment

All patients will be registered through the Clinical Trials Office at Montefiore Medical Center. On Study Form and the signed Patient Consent Form must be emailed to the clinical trials office at Montefiore Medical Center, [contact], at the time of registration and prior to patient treatment. At the same time, patient will be registered into the Velos system at ctms.montefiore.org. Recruitment will occur during standard of care visits by the treating physician. At the time of registration, all eligibility criteria must be checked. Patients must meet all of the eligibility requirements listed in Section 3.1. Data collection must not start prior to registration. It is the study coordinator's responsibility to review all data submitted to Velos and the Clinical Trials Office for accuracy and completeness, and he/she must sign off on the study form.

7.0 DATA HANDLING AND RECORD KEEPING

7.1 Confidentiality

Information about study subjects will be kept confidential and managed according to the requirements of the Health Insurance Portability and Accountability Act of 1996 (HIPAA). Those regulations require a signed subject authorization informing the subject of the following:

- What protected health information (PHI) will be collected from subjects in this study
- Who will have access to that information and why
- Who will use or disclose that information
- The rights of a research subject to revoke their authorization for use of their PHI.
- In the event that a subject revokes authorization to collect or use PHI, the investigator, by regulation, retains the ability to use all information collected prior to the revocation of subject authorization.

For subjects that have revoked authorization to collect or use PHI, attempts should be made to obtain permission to collect at least vital status (i.e. that the subject is alive) at the end of their scheduled study period.

7.2 Source Documents

Source data is all information, original records of clinical findings, observations, or other activities in a clinical trial necessary for the reconstruction and evaluation of the trial. Source data are contained in source documents. Examples of these original documents, and data records include: hospital records, clinical and office charts, laboratory notes, memoranda, subjects' diaries or evaluation checklists, pharmacy dispensing records, recorded data from automated instruments, copies or transcriptions certified after verification as being accurate and complete, microfiches, photographic negatives, microfilm or magnetic media, x-rays, subject files, and records kept at the pharmacy, at the laboratories, and at medico-technical departments involved in the clinical trial.

7.3 Data Safety Monitoring

As this is not a therapeutic trial, regular review of study conduct, adverse events, and results by a Data Safety and Monitoring Board is not required.

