4.2 Study Design

Appetite Assessments

This study will utilize the validated Council of Nutrition appetite questionnaire (CNAQ) (Appendix 2) to evaluate the effect of the nutrition intervention and pharmacological agents on patients'

appetite and nutritional intake. The CNAQ has been used in many studies as a validated questionnaire to assess appetite. The patient populations in these studies have ranged from community-dwelling adults and nursing home residents to patients with chronic diseases like ALS.²⁵⁻²⁶ It has also been used as a validated analysis of appetite in studies with patients with liver cancer in Taiwan and head and neck cancer.²⁷⁻²⁸

The patients will fill out this questionnaire weekly to assess change. If the patient scores >28 on the CNAQ, then the questionnaire will be administered biweekly, as will the nutrition education.

Quality of Life Assessments

All participants will also be asked to complete a quality of life survey (Functional Assessment of Cancer Therapy-General Population (FACT-GP), Appendix 3) on a weekly or biweekly basis at the same time as the nutrition assessment. If a patient is not present in the Medical Oncology or Radiation Therapy at the time either assessment is due, the assessments will be performed over the phone.

FACT-GP measures quality of life by asking about physical, function, emotional, and social wellbeing. In its creation, the questionnaire was modified to so it can be applicable to the general cancer population. It has been used to assess quality of life in many different sites of cancer.²⁹⁻³³

Nutritional Status

Nutritional status will be determined based on the answers to the appetite assessment and quality of life questionnaire, as well as the nutrition assessment provided by the Registered Dietitian. No lab values will be used to assess nutrition status during the course of this study.

Algorithm

The patient care will follow a pathway based on their responses to the CNAQ and clinical judgment of the physician and dietitian. The patients with fair-good appetite (score on CNAQ >24) will not receive any pharmacological agents and will receive nutrition intervention alone. Nutrition intervention will be in accordance with the Academy of Nutrition and Dietetics guidelines. The intervention will involve “purposefully planned action(s) designed with the intent of changing a nutrition-related behavior, risk factor, environmental condition, or aspect of health status”³⁴.

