The patients with poor-fair appetite (score on CNAQ <24) will be provided nutrition intervention by the Registered Dietitian and then put into one of three pharmacological groups. If the patient’s prognosis is extremely poor (<12 weeks expected survival, based on discussion with the patient’s treating physicians) and there is no additional disease modifying therapy planned, the patient will be prescribed 4mg dexamethasone (which is FDA approved), once daily, to be taken orally in the morning. Dexamethasone is given to patients with a limited expected lifespans because it has been found to be effective on a short-term basis. Also, the long-term usage of steroids has been found to myopathy and other various side effects.³⁵

If a patient has a history of marijuana use or has tried it in the past, then he/she will be prescribed medical marijuana based on financial availability due to previous exposure exhibiting better tolerance to the drug. If the marijuana is not feasible, he or she will be prescribed dronabinol (which is FDA approved). Dronabinol is used as a substitute as it contains synthetic delta-9-tetrahydrocannabinol (THC), a substrate of marijuana and therefore has a similar affect to medical marijuana. Since dronabinol is compounded similarly to medical marijuana, then for this patient population the tolerance to the medication is likely to be good.³⁶⁻³⁸

If the patient does not have any history of marijuana use, mirtazapine will be prescribed. Mirtazapine has been show to improve both appetite and quality of like in cancer patients.³⁹⁻⁴¹ Dosing mirtazapine was determined by guidelines published by the US Department of Veterans Affairs/Department of Defense. If the patient is under the age of 70, then she/he would be prescribed 15mg of mirtazapine (which is FDA approved), once daily, to be taken orally at bedtime. For geriatric population (if the

patient is over the age of 70), then she/he would be prescribed 7.5mg of mirtazapine, once daily to be taken orally at bedtime.

Refer to the flowchart (Appendix 4) for the sample pathway.

Study Duration

The study period will begin after the initial screening and immediately following study registration and last for three months.

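### Section 7.3 waives DSMB review on a rationale that conflicts with section 4.2, and no visible section plans drug-related adverse events, reasons for stopping drug, or a named safety reviewer in its place

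*Combined protocol and SAP*

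**What the plan says.** Section 7.3 (Data Safety Monitoring) is a single sentence that gives its reason and conclusion together: "this is not a therapeutic trial, regular review of study conduct, adverse events, and results by a Data Safety and Monitoring Board is not required". This is the only place in the visible text where adverse events are mentioned.

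Section 4.2 (Study Design) describes the intervention:

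- The CNAQ is used "to evaluate the effect of the nutrition intervention and pharmacological agents on patients" (their appetite and intake).
- Patients scoring below 24 receive dietitian intervention and are then "put into one of three pharmacological groups". The drugs are dexamethasone, medical marijuana with dronabinol as substitute, and mirtazapine.
- Patients with past marijuana use are prescribed medical marijuana "based on financial availability due to previous exposure exhibiting better tolerance to the drug". On the dronabinol substitute, the section expects that "for this patient population the tolerance to the medication is likely to be good".
- On dexamethasone, it remarks that "the long-term usage of steroids has been found to myopathy and other various side effects".
- On contact frequency: "The patients will fill out this questionnaire weekly to assess change". This becomes biweekly above a score of 28, and FACT-GP is collected at the same contacts.
- On duration: "The study period will begin after the initial screening and immediately following study registration and last for three months".

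Section 5.0 (Statistical Considerations) defines the primary endpoint as giving the algorithm's intervention within 30 days of enrollment. It counts dropouts, and it describes the frequency of hydration episodes, emergency visits and admissions. Section 7.4 (Data Recording) lists four items per visit: CNAQ score, FACT-GP score, assessment date and medication provided.

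**The concern.** Two things do not fit together. First, the waiver rests on calling the study non-therapeutic, yet the protocol itself decides which patients start an appetite stimulant and which one, and it sets out to evaluate the effect. Inclusion criterion 3 excludes prior users of appetite stimulants, so for this purpose the drugs are new to the patients who receive them.

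Second, once the DSMB is set aside, no visible section says what takes its place. If sites follow 7.3 and 7.4 as written, harms thought to be related to a study-assigned drug, and the reasons a drug was stopped, are not systematically collected. An analyst cannot reliably rebuild that information afterwards. At stake are patient oversight and the reading of the feasibility result: a reader would learn how many patients were given the intervention, but not how many later stopped the drug or why.

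**Working it through.** **1. The plan's own figure.** The only design figure is the precision statement in 5.0: 30 patients, 85% success, exact interval 67% to 95%, width 28%. Clopper-Pearson limits with x = 0.85 × 30 = 25.5 and n = 30 are 67.3% and 95.3%, width 28.1%. The figure reproduces, and this point does not depend on it.

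**2. The rationale against the design.**

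| Section | Content | Fits a non-therapeutic label? |
|---|---|---|
| 2.1, 5.0 | Feasibility aim; endpoint is administration within 30 days | Yes, loosely |
| 4.2 | Evaluates the drugs' effect; assigns patients to drug groups | No |
| 4.3 | Primary endpoint is quality-of-life impact of an algorithm that includes appetite stimulants | No, but 4.3 itself conflicts with 5.0 |

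The contradiction rests on 4.2. Section 4.3 adds little, because reconciling it to 5.0 could remove it.

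**3. What is planned that bears on safety.**

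| Source | What it gives | What it lacks |
|---|---|---|
| 5.0, exploratory endpoints | Frequencies of hydration, emergency visits, admissions | Cause; link to drug |
| CNAQ and FACT-GP items | Repeated nausea, energy, pain, feeling ill, mood, sleep | Events; link to drug. 7.4 stores scores |
| 5.0, dropouts | Counts, percentages, intervals | Reasons |
| 4.1 | Reasons for declining to join | Reasons for stopping drug |
| 7.4, medication provided | May show that a drug ceased | Why |
| 7.2 | Generic list of source documents, including pharmacy records | Any plan to extract harms |

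No row supplies adverse events with possible relation to the assigned drug, stop reasons, or a reviewer.

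**4. What a safety table of this size could show.** With no events in n patients, the two-sided 95% exact upper limit is 1 − 0.025^(1/n). For n = 30 it is 11.6%. The documents give no branch sizes. Assuming 5 or 10 patients on one drug, it is 52.2% or 30.8%. Such a table can describe, but it cannot test tolerance.

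**5. Recording burden.** Three months = 3 × 365.25/12 = 91.3 days = 13.0 weeks. If all contacts are weekly, 30 × 13 = 390. If all are every two weeks, 30 × 6.5 = 195. At an assumed 2 to 5 minutes each, the range is 195 × 2/60 = 6.5 hours to 390 × 5/60 = 32.5 hours. The contact counts are upper bounds: they assume that all 30 patients stay three months and that all need the fields, whereas patients scoring above 24 receive no drug.

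**The case against.** The strongest reply is that 7.3 reaches an acceptable decision and only words it loosely. Aim 1 and the 5.0 endpoint concern feasibility, and a small single-site pilot does not need a DSMB. That stands: a reader might infer that a DSMB is required, and nothing in the documents supports this.

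A reader might also infer that safety is not looked at in any form. That goes too far. The utilization counts and repeated symptom items are real, if indirect, information. Criterion 5 screens for contraindications, and 6.2 allows immediate-hazard changes. Section 7.4 is not exhaustive, since it also omits outcomes that 5.0 reports. None of these, however, is a plan for follow-up of drug-related harms.

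A third tempting reading is that the feasibility rate is inflated by patients who start and then stop. One patient is 1/30 = 3.3 points, and 61.3 of 91.3 days (67%) fall after the 30-day window. But the endpoint is administration within 30 days, so such patients are correctly counted. These figures show no bias.

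Finally, one might say that expected tolerance drives drug assignment generally. Section 4.2 gives that reason for the marijuana/dronabinol branch only. Dexamethasone turns on prognosis and absence of further disease-modifying therapy, and mirtazapine on no marijuana history. Section 4.2 also leaves room for clinical judgment.

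**Conclusion.** The point holds in a limited form and should be fixed. The stated reason for the waiver conflicts with 4.2, and nothing visible replaces the review it waives. No number in the plan changes: the sample size, its precision and the primary rate are unaffected. How many patients will receive or stop a drug is not given, so no size of harm or misclassification is claimed.

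The contradiction rests on text that is fully visible. The absence of a replacement is less certain, because the consent pages and the Appendix 4 flowchart could not be read and might name a reviewer or a reporting route.

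**What to change.** - Reconcile the 7.3 rationale with 4.2, for example by basing the waiver on the small, single-site feasibility design.
- Add to the 7.4 record, at the existing weekly or biweekly contacts: adverse events with the investigator's judgment of relation to the assigned drug; and drug start date, stop date and stop reason.
- Tabulate these descriptively by algorithm branch beside the unchanged feasibility rate, with no inference about tolerance.
- State that the investigator reviews the cumulative table at set intervals and reports through the IRB.

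No DSMB, extra visit, dose or stopping rule is proposed. The cost is a wording amendment, a few spreadsheet columns, one table, and the contact time estimated above. The minutes per contact are an assumption, and judging relation to drug and the interval reviews add to them. Branch counts will be small and, in patients who may be on active cancer treatment, hard to attribute.

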Diarrhea: Yes/No

Feel full quickly: Yes/No

Fatigue: Yes/No

Ostomy: Yes/No

Open wound or ulcer: Yes/No

Visible cachexia/muscle wasting: Yes/No

Trouble buying food: Yes/No

Assessment Completed (Auto-Calculation):

Referral to Nutritionist

Referral:

Appendix 2

Council on Nutrition Appetite Questionnaire

- 1) My appetite is
 1. Very poor
 2. Poor
 3. Average
 4. Good
 5. Very good

- 2) When I eat, I feel full after
 1. Eating only a few mouthfuls
 2. Eating about a third of a plate/meal
 3. Eating over half of a plate/meal
 4. Eating most of the food
 5. Hardly ever

- 3) I feel hungry
 1. Never
 2. Occasionally
 3. Some of the time
 4. Most of the time
 5. All of the time

- 4) Food tastes
 1. Very bad
 2. Bad
 3. Average
 4. Good
 5. Very good

- 5) Compared to when I was younger, food tastes
 1. Much worse
 2. Worse
 3. Just as good
 4. Better
 5. Much better

- 6) Normally, I eat
 1. Less than one regular meal a day
 2. One meal a day
 3. Two meals a day
 4. Three meals a day
 5. More than three meals a day (including snacks)

7) I feel sick or nauseated when I eat

1. Most times
2. Often
3. Sometimes
4. Rarely
5. Never

8) Most of the time my mood is

1. Very sad
2. Sad
3. Neither sad nor happy
4. Happy
5. Very happy

TOTAL SCORE: _____

Scoring Total the score by adding the numbers associated with the patient's response. A score of less than 28 is cause for concern. If the total is 8-16, the patient is at risk for anorexia and needs nutrition counseling. 17-28, the patient needs frequent reassessment. >28, the patient is not at risk at this time.

Appendix 3:

FACT-GP (Version 4)

Below is a list of statements that other people have said are important. **Please circle or mark one number per line to indicate your response as it applies to the past 7 days.**

PHYSICAL WELL-BEING		Not at all	A little bit	Some -what	Quite a bit	Very much
G P 1	I have a lack of energy	0	1	2	3	4
G P 2	I have nausea	0	1	2	3	4
G P 3	Because of my physical condition, I have trouble meeting the needs of my family	0	1	2	3	4
G P 4	I have pain	0	1	2	3	4
G P 6	I feel ill	0	1	2	3	4
G P 7	I am forced to spend time in bed	0	1	2	3	4

SOCIAL/FAMILY WELL-BEING		Not at all	A little bit	Some -what	Quite a bit	Very much
G S 1	I feel close to my friends	0	1	2	3	4
G S 2	I get emotional support from my family	0	1	2	3	4
G S 3	I get support from my friends	0	1	2	3	4
G S 6	I feel close to my partner (or the person who is my main support)	0	1	2	3	4

Q
1
Regardless of your current level of sexual activity, please answer the following question. If you prefer not to answer it, please mark this box and go to the next section.

G I am satisfied with my sex life 0 1 2 3 4
S
7

EMOTIONAL WELL-BEING

		Not at all	A little bit	Some -what	Quite a bit	Very much
G	I feel sad	0	1	2	3	4
E					
1						
G	I feel nervous	0	1	2	3	4
E					
4						
G	I worry about dying	0	1	2	3	4
E					
5						
G	I worry that my condition will get worse	0	1	2	3	4
E					

FUNCTIONAL WELL-BEING

		Not at all	A little bit	Some -what	Quite a bit	Very much
G	I am able to work (include work at home)	0	1	2	3	4
F					
1						
G	My work (include work at home) is fulfilling	0	1	2	3	4
F					
2						
G	I am able to enjoy life	0	1	2	3	4
F					
3						
G	I am sleeping well	0	1	2	3	4
F					
5						
G	I am enjoying the things I usually do for fun	0	1	2	3	4
F					
6						
G	I am content with the quality of my life right	0	1	2	3	4
F	now					

Appendix 4
